	Personal identifiers and/or codes linking the data and/or specimens to personal identifiers will be maintained for future research.
	Audio or Video recordings will be transcribed and then destroyed or modified to eliminate the possibility that study participants could be identified.
ı	Photos or Images will be modified to eliminate the possibility that study participants could be identified.
	Restricted use data will be destroyed or returned to the source.
	1.1 If you indicated that personal identifiers will be maintained for future research, provide the following information: a) How the information will be securely handled and stored b) assure confidentiality, and c) who will have access to the identifiers and/or codes. Once the research described in this study is completed, we will destroy the key linking patient names and identifiers to the data used for analysis. The de-identified data or spreadsheet used for analyses will be retained for 1-2 years after the study results are published.
2.0	Describe any additional steps, if any, to be taken to assure that the subjects' identities and any personal identifying information are kept confidential.
ID: IRB	\$17-000048 View: NEW 9.6 - Use of Data and/or Specimens without Direct Contact

This view has been locked by amendment(s)

Warning: Save your work at least every 15 minutes by clicking "Save" or "Continue."

Use of Data and/or Specimens without Direct Contact

You indicated that some or all of the research activities do not involve direct contact with study participants (Section 8.1/item 1.0). Please provide the following information.

1.0 If all of your research activities are without direct contact with study participants, provide the following information:

1.1 Indicate the purpose of the research, specifying the problems and/or hypotheses to be addressed:

The purpose of our study is to analyze preoperative, intraoperative, and postoperative outcomes in patients treated with selective (doxazosin) or non-selective (phenoxybenzamine) alpha blockade prior to pheochromocytoma resection. Outcomes will include postoperative morbidity and mortality, intraoperative hemodynamic instability, quality of life, and cost.

We hypothesize that doxazosin is not inferior compared to phenoxybenzamine in terms of postoperative morbidity and mortality, intraoperative hemodynamic instability, quality of life, and cost.

1.2 Describe the study design and proposed data analyses:

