Given the difficulty in randomizing patients (high cost of phenoxybenzamine has caused a large portion of patients crossing over to the doxazosin arm, resulting in unbalance between the number of patients in each arm), patients who have been pre-treated with doxazosin before pheochromocytoma resection prospectively followed during the course of this study will be compared to a retrospective group of patients who were pre-treated with phenoxybenzamine.

Descriptive statistics including mean, median, standard difference, and frequencies will be calculated for each of the variables measured.

Differences in hemodynamic instability as indexed by specific vital sign parameters, ICU length of stay, inpatient length of stay, morbidity, mortality, cost, and quality of life will be analyzed with t tests or non-parametric tests as appropriate.

1.3 *If you will conduct genetic analysis with specimens, provide your assurance that the results will not be disclosed to subjects or used for clinical care.

Agree	
Not Applicable	

2.0 *Describe specimens and/or data that will be acquired without direct contact with study participants. Complete this item for each type used in the study:

usea in the stu	uy.	
Source	Data and/or Specimens Information	
View UCLA medical records	Data and/or Specimens? Indicate all that apply:	Data
	Indicate whether the data and/or specimens are pre-existing, at the time of this study, and/or if collection will be prospective:	Pre-existing
	Describe the data and/or specimens and indicate the original collection dates:	Electronic medical records from patients undergoing adrenalectomy for pheochromocytoma or paraganglioma from January 1, 2015 to present. Please see item 4.0 for further details on data to be collected from the EMR.
	Indicate the approximate number of data records and/or specimens to be collected:	50
	Will the specimens be used with animals?	No
	If yes, indicate the IACUC Number:	No Value Entered

*If any sources of data and/or specimens are not at UCLA, provide your agreement that the appropriate institutional approvals for release will be obtained (e.g., IRB approval).

Agree

•	
Not Applicable	
	o third parties, please contact the CTSI for directions about additional requirements. sources/pages/third_party
nttps://www.ctsi.ucla.edu/researcher-re	sources/pages/third_party
uttps://www.ctsi.ucla.edu/researcher-re	

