INTRAOPERATIVE PROTOCOL. Intraoperative hemodynamic monitoring will be conducted in the standard fashion, and a phenylephrine dose response curve will be generated by titration with phenylephrine to estimate the ED30 and therefore the effectiveness of the blockade. Surgery will proceed in the standard fashion. Times of induction, tumor manipulation, and adrenal vein ligation will be recorded. Vasopressors will be used at the discretion of the anesthesiologist.

POSTOPERATIVE PROTOCOL. Patients will be taken to the PACU for routine postoperative care. Admission to the surgical ICU will be performed at the discretion of the attending anesthesiologist and surgeon.

QUALITY OF LIFE / DRUG ADVERSE EFFECTS. Data regarding patient health related quality of life and drug adverse effects will be collected at five time points pre-blockade, post-blockade, and postoperatively at 3 months, 6 months, and 1 year. Health related quality of life data will be assessed utilizing the Short Form-36. Patients will be queried to specific adverse effects such as nasal congestion, headaches, palpitation, as well as their frequency and level of distress caused. Surveys will be complete in person during routine encounters or over the phone.

COST. Preoperative drug costs will be determined using the average wholesale price per unit multiplied by the number of units taken by the patient. Enrollment of the patient in Medicare and Medicare part D will be noted. Data regarding out of pocket drug costs will be collected. Inpatient costs will be calculated utilizing patient charges and the application of a charge to cost ratio.

4.1	* Will you be providing results of any experimental tests that
	are performed for the study?

o	Not Applicable
0	No
0	Yes - Complete Items 4.1.1 and 4.1.2

- 4.1.1 You indicated in Item 4.1 that the research involves experimental tests. Please describe the tests, provide a rationale for providing participants with the experimental test results and explain what, how and by whom participants and their health care provider will be told about the meaning, reliability, and applicability of the test results for health care decisions.
- 4.1.2 Will tests be performed by a Clinical Laboratory Improvement Amendments (CLIA) approved lab?

 Yes No

$^{5.0}$ *Indicate how much time will be required of the subjects, per visit or contact, and in total for the study.

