- (1) Cost. The cost of prescription drugs in the United States is increasing, with the cost of some drugs increasing by over 1000% in the last decade.[1] Currently, the maximum listed wholesale price per unit of phenoxybenzamine is \$197.79 in contrast to \$1.42 for doxazosin[2]. In our anecdotal experience, an increasing number of patients are unable to afford phenoxybenzamine for preoperative alpha blockade prior to pheochromocytoma resection. As current studies show no differences in morbidity and mortality between selective and non-selective alpha blockade prior to pheochromocytoma resection, doxazosin is likely to represent a clinically equivalent option associated with significant cost savings.
- (2) Quality of life. Phenoxybenzamine is a long-acting, non-competitive, non-selective alpha blocker that crosses the blood brain barrier, causing centrally mediated side effects including headaches and sedation that limit the medication's tolerability. Patients who receive doxazosin in comparison to phenoxybenzamine prior to pheochromocytoma resection less frequently experience postural hypotension, nasal stuffiness, and headache.[3] In addition to being cost effective, doxazosin may also be associated with increased health related quality of life while receiving alpha blockade.

Overall, current retrospective data suggest that selective alpha blockade is as effective as non-selective blockade in addition to being less costly and associated with less frequent adverse effects. A randomized controlled trial demonstrating this will result in societal cost savings and increased health related quality of life in patients undergoing pheochromocytoma resection.

- [2] http://micromedex.com/Portals/1/Assets/AWP%20Policy_Oct%202014.pdf

Risks

*Indicate the potential risks/discomforts, if any, associated with each intervention or research procedure.

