Additionally discuss any measures that will be taken to minimize risks. If data are available, estimate (a) the probability that a given harm may occur, (b) its severity, and (c) its potential reversibility. The information provided should be reflected in risks section of the informed consent documents.

If this is an exempt study and there are no risks, indicate N/A. Otherwise, please see the help text. The potential risks of the study include the following:

LOSS OF CONFIDENTIALITY: Although patient identifiers and data will be stored on a secure server with limited access, basic contact information such as the patient's name, address, and telephone number may be at risk if the server is compromised.

STANDARD OF CARE DRUG RISKS: Since both drugs are standardly used to prepare patients for pheochromocytoma surgery, participating in this research study will not expose patients to additional risks beyond what is considered standard of care. Studies comparing phenoxybenazime and doxazosin have mostly shown no difference in blood pressure fluctuations during surgery.

Risk/Benefit Analysis

4.0 *RISKS/BENEFIT ANALYSIS: Indicate how the risks to the participants are reasonable in relation to anticipated benefits, if any, to participants and the importance of the knowledge that may reasonably be expected to result from the study:

Current retrospective data suggest that selective alpha blockade is as effective as non-selective blockade in addition to being less costly and associated with less frequent adverse effects. A randomized controlled trial demonstrating this will result in societal cost savings and increased health related quality of life in patients undergoing pheochromocytoma resection.

Alternatives

5.0 *Indicate the alternatives to participating in this study.

Check all that apply.

	All types	s of studies - Choose not to participate in the study
		ntervention Studies - Receive standard of care instead of participating in the study
		ntervention Studies - Medication, device, or other treatment is available off study
		lot Applicable (e.g., study of existing data)
⊢	Other	The state (sign) state of stat
	0	
	5.1	If "other" was selected, specify.
	5.2	If this is a clinical/intervention study:
		Describe the standard of care or activities at UCLA (or study
		site) that are available to prospective participants who do not enroll in this study. If not applicable to your study, state not

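### The plan commits to no difference in mean cost with a confidence interval, and leaves open a rank test that does not address mean cost

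*Combined protocol and SAP*

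**What the plan says.** NEW 9.6, item 1.2 (study design and proposed data analyses) lists hemodynamic instability, lengths of stay, morbidity and then "mortality, cost, and quality of life will be analyzed with t tests or non-parametric tests as appropriate". It gives no criterion for choosing between the tests and names no non-parametric test. The same item says: "Descriptive statistics including mean, median, standard difference, and frequencies will be calculated for each of the variables measured". The statistics item of NEW 10.1 repeats that sentence. Neither mentions an interval for any outcome.

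NEW 10.1, item 4.0 (COST) builds cost from two parts. For drugs: "Preoperative drug costs will be determined using the average wholesale price per unit multiplied by the number of units taken by the patient". For the hospital stay: "Inpatient costs will be calculated utilizing patient charges and the application of a charge to cost ratio". The benefits text (Risks & Benefits, item 2.0) says "the maximum listed wholesale price per unit of phenoxybenzamine is" $197.79, against $1.42 for doxazosin.

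The hypothesis in NEW 9.6, item 1.1 is one of non-inferiority: "We hypothesize that doxazosin is not inferior compared to phenoxybenzamine in terms of postoperative morbidity and mortality", with cost later in the same list and no margin given. Risks & Benefits, items 2.0 and 4.0, say that a trial demonstrating equal effectiveness at lower cost "will result in societal cost savings and increased health related quality of life".

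**The concern.** A societal saving is an aggregate, so it depends on the difference in mean cost per patient. A rank test asks instead whether a patient drawn from one group tends to cost less than a patient drawn from the other. It gives little extra weight to how expensive the most expensive patients are. Here the two can part company: the drug price gap lowers cost for nearly every doxazosin patient, while ICU admission (discretionary under NEW 10.1) and long stays can add large sums for a few.

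The substantive cost question is whether the cheaper drug is still cheaper once those few stays are counted. A rank test could answer yes when the means say no. Because the test is left to be judged appropriate later, it may also be chosen after the data are seen. Whichever test is used, the plan promises no saving per patient with a statement of its uncertainty.

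**Working it through.** **Plan's own figures.** No figure is stated for the cost comparison. The only derived size is the screening number: 62 / 0.85 = 72.9, rounded up to 73, which reproduces. No power, SD or effect size is given for the 62.

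**Inputs from the documents.** Unit prices of $197.79 and $1.42 (maximum listed wholesale prices); a maximum enrolment of 62; about 50 retrospective records.

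**Assumptions.** The documents give no cost distribution, unit counts, complication costs or doxazosin group size. I assume lognormal inpatient cost, 21 to 63 drug units, two-sided 0.05, and two pairs of group sizes: 31 v 31 (the 62 split equally) and 62 v 50 (doxazosin first). Neither pair is a documented comparison. Unit counts are for illustration and imply nothing about dosing.

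**1. Targets.** Societal saving = N × (mean cost on phenoxybenzamine − mean cost on doxazosin). Mann-Whitney tests whether P(doxazosin patient costs less) + ½P(tie) = ½. These agree under a pure shift, but not in general.

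**2. Drug cost alone.** Price ratio 197.79 / 1.42 = 139. Difference per unit 197.79 − 1.42 = $196.37. Over 21, 42 and 63 units this is $4,124, $8,248 and $12,371 per patient. With similar unit counts, ranks and means agree.

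**3. Total cost, same inpatient distribution in both groups.** With 42 units, inpatient mean $20,000, log-SD 0.6 and 62 v 50, Mann-Whitney is significant in 99% of trials and Welch's t test in 90%. Both point to doxazosin as cheaper, and the rank test has more power.

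**4. Total cost, expensive stays in one group only.** With 42 units, inpatient mean $20,000, log-SD 0.4 and an 8% chance of a further $150,000 on doxazosin only, the true mean difference is 0.08 × 150,000 − 42 × 196.37 = 12,000 − 8,248 = $3,752, so doxazosin is dearer.

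| Groups | Mann-Whitney declares doxazosin cheaper | Welch declares doxazosin cheaper |
|---|---|---|
| 31 v 31 | 87% | 7% |
| 62 v 50 | 99% | 2% |

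**5. Equal medians, heavier tail in one group (62 v 50).** Mean ratio = exp[(s₁² − s₂²)/2].

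| log-SDs | Mean ratio | Mann-Whitney rejects | Welch rejects |
|---|---|---|---|
| 0.9 v 0.5 | exp(0.28) = 1.32 | about 5% | about 33% |
| 1.0 v 0.5 | exp(0.375) = 1.45 | about 5% | about 45% |

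Here the rank test rejects at about its false-positive rate although the means differ by 32% or 45%. This case ignores the drug price gap, so it shows the mechanism only; it is not a forecast.

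**6. Is a t test enough?** Take step 4 with a 5.5% chance of the expensive stay. The mean difference is 0.055 × 150,000 − 8,248 = $2, effectively none. Welch still declares doxazosin cheaper in 17% (31 v 31) and 9% (62 v 50) of trials, against a nominal 2.5%. Fixing the t test alone would not settle the matter.

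**The case against.** A reader might infer that the plan sends cost to a rank test. It does not say so: there is no skewness or normality rule, no rank test is named, and the t test stays open. Choosing a rank test for skewed costs is the usual reading of such wording, but it is an inference. Skewness itself is plausible rather than documented.

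A reader might also infer that the plan yields no cost estimate and so cannot support a saving. That goes too far. Means are promised for every measured variable, so each group's mean cost, and hence the difference, will be available. What is missing is the interval and a commitment to the mean as the target of inference.

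The saving is claimed in the benefits narrative, whereas the formal hypothesis is non-inferiority on a list that includes cost. This stands, but with no margin stated, a non-inferiority claim on cost needs an estimate and interval even more than a superiority claim would.

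The strongest objection concerns size. Reversal needs a heavier cost tail in the doxazosin group specifically, and nothing in the documents says there will be one. With the same inpatient distribution in both groups the rank test loses nothing (step 3). So the wrong-direction result is a possibility under assumptions and should not be read as an expected outcome.

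**Conclusion.** The concern holds in a limited form. The plan specifies no difference in mean cost with a confidence interval, and it permits a test that does not address the mean, while the stated societal benefit depends on the mean. How much this matters turns on inpatient cost distributions that the documents do not give. It is nothing to speak of if the two groups share a distribution. If rare expensive stays fall mainly on one side it can be serious: in the assumed example, doxazosin is called cheaper in 87% to 99% of trials although it is $3,752 dearer on average. The descriptive means keep the question answerable in part. This is an inexpensive improvement to one of several outcomes and not a threat to the study as a whole.

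**What to change.** In NEW 9.6, item 1.2 and the statistics item of NEW 10.1, take cost out of the shared list and pre-specify:

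- **Primary cost estimate:** the difference in arithmetic mean total cost per patient (drug plus inpatient) with a bootstrap 95% confidence interval.
- **Adjusted version:** the same contrast from a covariate-adjusted model, for example a gamma GLM, using named baseline variables already being collected. This should be required, because item 1.2 now compares a prospective doxazosin group with retrospective phenoxybenzamine patients and an unadjusted difference would not isolate the drug.
- **Presentation:** drug and inpatient cost shown separately as well as summed; medians as description only.

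The cost is a few sentences and routine computing, with no new data. There are two downsides to state in the plan. The interval will be wider than a rank-test result might suggest. Bootstrap coverage may also fall somewhat below 95% in small, heavily skewed groups: under the lognormal assumptions of step 5, a bias-corrected and accelerated interval covered in about 90–92% of runs at 62 v 50 and 87–90% at 31 v 31.

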PATIENT ACQUISITION. All patients referred to the UCLA Department of Surgery requiring surgical resection of pheochromocytoma or paraganglioma will be counseled about surgery and the necessity for preoperative alpha blockade. The benefits and risks of the study will discussed, and the patient will be given the opportunity to enroll. Upon obtaining informed consent regarding enrollment in the study, the patient will be randomized to either receive preoperative blockade with either phenoxybenzamine or doxazosin.

PREOPERATIVE PREPARATION. The patient will then be referred to the UCLA Preoperative Evaluation and Planning Center (PEPC) for preoperative planning and optimization by an attending anesthesiologist. Additional testing such as echocardiography or stress testing will be pursed in accordance with preoperative risk-stratification in the standard fashion. A few weeks prior to surgery, the patient will initiate preoperative alpha blockade with the drug as determined by randomization. The drug will be titrated to a blood pressure of 120-130/80-85 in the standard fashion. Adjunctive beta blockers or calcium channel blockers may be initiated at the discretion of the physician.

Titration will be performed utilized the attached log ("Medication and Blood Pressure Log"), which will be emailed to the patient and will be returned by the patient by email every 2 days. The patients sitting and standing blood pressure will be used to titrate their alpha blocker dosage to prespecified targets as noted in the original IRB proposal. Heart rate will be logged to determine whether the patient requires adjunctive

specified targets as noted in the original IRB proposal. Heart rate will be logged to determine whether the patient requires adjunctive antihypertensive medications such as beta blockers or calcium channel blockers. This titration will take place over a period of 2-3 weeks. Once the patient's alpha blockade titration is complete, the log will be saved in a secure, encrypted server and will be linked with the patients record using non-identifying record ID.

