The time required of study subjects will includes time that will be standard for the care of the patient and unrelated to participation of the study. This involves preoperative evaluation by a surgeon (30 minutes) and anesthesiologist (30 minutes), inpatient surgery and routine inpatient postoperative care (average length of inpatient stay 2-3 days), and postoperative follow up (30 minutes).

Additional time required of the study subjects as related to the study would involve 5 questionnaires administered in person or by phone at the time points outlined above, with each administration of the survey taking approximately 5 minutes.

*Statistics and Data Analysis: Describe the proposed statistical procedures or descriptive analyses for the study. If applicable, indicate how the sample size was determined.

Descriptive statistics including mean, median, standard difference, and frequencies will be calculated for each of the variables measured.

This view has been locked by amendment(s)

Warning: Save your work at least every 15 minutes by clicking "Save" or "Continue."

Characteristics of the Study Population

1.0 *Is this an observational or ethnographic study for which the number of participants observed or interviewed cannot be determined in advance.

O Yes O No

- 2.0 If you answered "no" to item 1.0, indicate the maximum number of study participants you hope to enroll: 62
- 3.0 How many participants do you expect you will need to recruit, consent and/or screen to meet the target number above?
- *Indicate the specific inclusion criteria for enrollment of each of the groups of research participants in this study.

 If there are any inclusion criteria based on *gender, pregnancy/childbearing potential, race, ethnicity or language spoken*, explain the nature of and scientific rationale for the inclusions.

 Inclusion criteria include:

(1) Diagnosis of pheochromocytoma or paraganglioma as evidenced by appropriate biochemical evaluation and imaging.

- (2) Surgical resection recommended.
- (3) Patients aged 12 and older.
- *Indicate the specific exclusion criteria for each of the groups of research participants in this study.

 If there are any exclusion criteria based on gender, pregnancy/childbearing potential, race, ethnicity or language spoken, explain the nature of and scientific rationale for the exclusions.

 None.
- 6.0 *How (chart review, additional tests/exams for study purposes, etc.), when and by whom will eligibility be determined?

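### The control records are drawn from adrenalectomies, while prospective patients enter on any recommended pheochromocytoma or paraganglioma resection, so the two groups may differ in operation and tumour site

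*Combined protocol and SAP*

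**What the plan says.** Section 9.6, item 1.2 sets out the current comparison. One group is "patients who have been pre-treated with doxazosin before pheochromocytoma resection prospectively followed during the course of this study"; these "will be compared to a retrospective group of patients who were pre-treated with phenoxybenzamine". The outcomes listed there are hemodynamic instability, ICU and inpatient stay, morbidity, mortality, cost and quality of life, to be compared with t tests or non-parametric tests.

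The retrospective source is described in section 9.6, item 2.0 as "Electronic medical records from patients undergoing adrenalectomy for pheochromocytoma or paraganglioma from January 1, 2015 to present". The same line is repeated in the detailed view of that item at the end of the document. The records are marked as pre-existing, and about 50 are expected.

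Prospective entry is described in two places. Section 10.1, under Patient Acquisition, takes "All patients referred to the UCLA Department of Surgery requiring surgical resection of pheochromocytoma or paraganglioma". Characteristics of the Study Population, item 4.0, requires "Diagnosis of pheochromocytoma or paraganglioma as evidenced by appropriate biochemical evaluation and imaging", then "Surgical resection recommended", and age 12 or older. Item 5.0 lists no exclusions.

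**The concern.** The record source names one operation. Prospective entry covers every resection of either tumour. A paraganglioma outside the adrenal is not removed by adrenalectomy, so on the literal wording such a case has a route into the doxazosin group and none into the controls.

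The type and site of operation can plausibly affect instability, ICU use, length of stay, morbidity and cost, which are the outcomes to be compared. The tests in item 1.2 are unadjusted, and the available text gives no matching or restriction by operation or tumour site. The stated hypothesis is that doxazosin is not inferior. A difference in case mix could make doxazosin look worse than it is, or could hide a real disadvantage.

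The plan already concedes the loss of randomisation. This imbalance is separate: it comes from how the cohorts are selected, and the investigators can remove it.

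**Working it through.** **The plan's own figure.** The only stated number with inputs near this point is the screening number: 62 / 0.85 = 72.94, rounded up to 73, as the plan says. It is correct and does not bear on the point. The point is checked by comparing the definitions.

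**Definitions side by side.**

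- Operation: adrenalectomy in the record source (section 9.6, item 2.0); any resection in prospective entry (section 10.1, Patient Acquisition).
- Tumour: both name pheochromocytoma and paraganglioma, but the record source reaches paraganglioma only through adrenalectomy.
- Surgical status: performed in the record source; recommended in the inclusion criteria. The comparison sentence in item 1.2, however, describes the doxazosin group as pre-treated before resection, which most naturally means operated patients.
- Drug: phenoxybenzamine for the controls and doxazosin for the prospective group (item 1.2).
- Separate eligibility list for the retrospective group: none in the available text. Item 2.0 refers to an item 4.0 for the data to be collected. The item 4.0 text in section 10.1 describes the randomised pathway and gives no rule for selecting records.

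Operation and tumour site are therefore not aligned, and nothing else in the available text aligns them.

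**Possible size, for illustration only.** Let r be the event risk after adrenalectomy, d the difference in risk after a non-adrenalectomy resection, and q the share of such resections in the doxazosin group. The controls have a share of zero on the literal reading. With no drug effect:

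- doxazosin risk = (1 − q) × r + q × (r + d) = r + q × d
- control risk = r
- spurious difference = q × d

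The documents give neither q nor d, so both are assumed:

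- q = 0: 0 points for any d
- q = 5%, d = 5 points: 0.05 × 5 = 0.25 points
- q = 10%, d = 20 points: 0.10 × 20 = 2 points
- q = 25%, d = 20 points: 0.25 × 20 = 5 points
- q = 30%, d = 30 points: 0.30 × 30 = 9 points

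The sign follows the sign of d, which is also unknown. The formula applies to event risks. For length of stay or cost, d would be a difference in mean days or in money.

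**Assignment of patients.** The record window runs to the present, so it overlaps enrolment. Item 1.2 reports that a large portion of patients crossed over to doxazosin, and section 20.1, item 1.1 refers to patients randomised to either drug. The available text does not say whether an enrolled phenoxybenzamine patient becomes a control, or where a patient who took both drugs belongs.

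**The case against.** The strongest reply is that adrenalectomy is loose shorthand for resection. The same line names paraganglioma, and it sits in a form field describing records to be accessed, so it is not a formal eligibility rule. The comparison sentence mentions pheochromocytoma resection only, and the attached study-variables and timeline files are not available here. This reply stands to the extent that the difference in operation is possible and has not been established. It does not remove the point. The line appears twice, it is the only operational description of the source apart from the drug received, and a query run as written would select by adrenalectomy. If the comparison sentence were read strictly, the doxazosin group would exclude paraganglioma while the record source names it, so the groups would still not be defined on common terms.

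A reader might infer three stronger things, which the documents do not support.

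- *The groups differ in surviving to surgery.* Item 1.2 describes the doxazosin patients as pre-treated before resection. Instability, ICU stay and 30-day postoperative mortality can be observed only after an operation. What remains is narrower: quality of life, adverse effects and drug cost have preoperative parts (section 10.1), and the plan does not say how enrolled but unoperated patients are handled for these.
- *Enrolled patients are counted twice, each making up 2% of the controls.* The groups are split by drug, so an enrolled doxazosin patient whose chart is pulled does not become a phenoxybenzamine control. Double counting would need a patient exposed to both drugs and placed in both groups. The 2% (1/50) treats all 50 records as controls, which the plan does not say.
- *The controls have no age limit.* The record line gives none, but the inclusion item asks for criteria for each group of participants and gives one list, with age 12 or older. Whether that list reaches the chart cohort is arguable.

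**Conclusion.** The point holds as a mismatch in the stated selection of the two groups. Taken literally, resections of paraganglioma outside the adrenal can enter the doxazosin group but not the phenoxybenzamine controls. The groups may therefore differ in operation and tumour site, and the unadjusted tests would attribute any resulting difference to the drug.

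The size cannot be estimated from the documents. The 0 to 9 point range above rests wholly on assumed shares and risk differences, includes zero, and has no known direction. The conclusion assumes that the record query is run as worded and that operation or site affects at least some of the outcomes. It should be corrected because the comparison is not randomised and this source of bias is avoidable.

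**What to change.** Define one analysis population and apply it to both groups: confirmed pheochromocytoma or paraganglioma, age 12 or older, preoperative alpha blocker started, and the same defined resection performed. There are two ways to align the operation:

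- widen the record query from adrenalectomy to any resection of these tumours; or
- restrict both groups to adrenalectomy.

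State a rule that assigns each patient to one group only. It should cover enrolled phenoxybenzamine patients and those who switched drugs. Report enrolled but unoperated patients separately for quality of life, adverse effects and drug cost.

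The cost is one revised query line and one analysis-set definition. The downside is a slightly larger chart pull under the first option, or the loss of a few extra-adrenal cases under the second. Clinical management does not change.
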